4.3.6. Duration of Nivolumab

Nivolumab will be given for a total of 15 doses (1 before RT, 4 during radiation therapy and 10 following completion of radiation), or until progressive disease, unacceptable toxicity, withdrawal of consent, or the study ends, whichever occurs first. For all subjects, global

deterioration of health status requiring discontinuation of treatment without objective evidence of disease progression at that time is allowed, if necessary.

4.3.7. Patient Reported Outcomes (PROs)

The FACT-HN and FACT-G (Appendix 2) Quality of Life (QOL) assessments will be performed at baseline, end of IMRT, and weeks 18, 30, 52, and 104. Patients who do not have QOL collected or refuse QOL completion will not be considered a protocol deviation. Paper or electronic questionnaires may be completed by the patient. A copy of the responses needs to be kept in the study subject's research binder.

4.3.8. Nivolumab Dose Levels

There will be no dose reductions allowed for nivolumab; delays will be allowed as detailed in the section describing nivolumab administration.

4.3.9. Nivolumab Packaging, Labelling, and Storage

Please refer to the Investigators Brochure for detailed information. Medication numbers will be unique to each bottle and will be used for tracking purposes only.

Supply

Nivolumab is supplied in a 100 mg/ 100 ml solution in a single use vial.

Storage Conditions

Nivolumab must be stored in accordance with the instructions on the label (Refer to investigator brochure. Supplies must be kept refrigerated (2 – 8 deg C). Do not freeze and protect from light).

Drug Accountability

Investigational supply of Nivolumab is obtained from Bristol Myers Squibb. Drug supplies, will be kept in a secure, limited access storage area under the storage conditions. Where necessary, a temperature log must be maintained to make certain that the drug supplies are stored at the correct temperature.

The responsible person must maintain records of the product's delivery to the study site, the inventory at the site and the use by each patient. The Principal Investigator (and participating site investigators) are responsible for all destructions/disposals of partially used and unused supplies. Supplies are not to be shipped back to BMS. BMS only needs to be notified of destructions/disposals of partially used samples. A copy of the drug destruction certificate must be maintained for provision to BMS at the end of the study.

These records will include dates, quantities, batch/serial numbers, expiry ("use by") dates, and the unique code numbers assigned to the investigational product(s) and study patients. The responsible person will maintain records that document adequately that the patients were provided the doses specified by the CSP and reconcile all investigational product(s) received from BMS. The responsible person must verify that all unused or partially used drug supplies have been returned by the clinical study patient.

4.4. MANAGEMENT OF SIDE EFFECTS FOLLOWING TREATMENT WITH NIVOLUMAB

4.4.1. Management of immunological toxicities following treatment with nivolumab

A proactive and early approach to management of immunological toxicities is crucial. The toxicities can be managed by a variety of treatment options to relieve symptoms and to reduce the risk of worsening symptoms.

4.4.2. Management of non-immunological toxicities following treatment with nivolumab

A proactive and early approach to management of immunological toxicities is crucial. The toxicities can be managed by a variety of treatment options to relieve symptoms and to reduce the risk of worsening symptoms.

4.4.4. Treatment Compliance

Records of study medication used, dosages administered and intervals between visits will be recorded by study personnel.

4.5. ENDPOINTS OF SAFETY

Safety of nivolumab will be evaluated as indicated by intensity and incidence of adverse events, graded according to US NCI CTCAE Version 4.03. Safety endpoints include:

- Events leading to dose holding
- Events leading to permanent treatment discontinuation
- The overall incidence and CTC criteria grade of adverse events, as well as relatedness of adverse events to treatment
- Causes of death

5. ADVERSE EVENTS DEFINITIONS AND REPORTING

5.1. ADVERSE EVENT DEFINITION

An **Adverse Event (AE)** is defined as any new untoward medical occurrence or worsening of a preexisting medical condition in a clinical investigation participant administered study drug and that does not necessarily have a causal relationship with this treatment. An AE can therefore be any unfavorable and unintended sign (such as an abnormal laboratory finding), symptom, or disease temporally associated with the use of investigational product, whether or not considered related to the investigational product.

Adverse events can be spontaneously reported or elicited during open-ended questioning, examination, or evaluation of a subject. (In order to prevent reporting bias, subjects should not be questioned regarding the specific occurrence of one or more AEs.)

5.2. SERIOUS ADVERSE EVENT DEFINITION

A **Serious Adverse Event (SAE)** is any untoward medical occurrence that at any dose:

- results in death
- is life-threatening (defined as an event in which the participant was at risk of death at the time of the event; it does not refer to an event which hypothetically might have caused death if it were more severe)
- requires inpatient hospitalization or causes prolongation of existing hospitalization (see NOTE below)

- results in persistent or significant disability/incapacity
- is a congenital anomaly/birth defect
- is an important medical event (defined as a medical event(s) that may not be immediately life-threatening or result in death or hospitalization but, based upon appropriate medical and scientific judgment, may jeopardize the subject or may require intervention [eg, medical, surgical] to prevent one of the other serious outcomes listed in the definition above.) Examples of such events include, but are not limited to, intensive treatment in an emergency room or at home for allergic bronchospasm; blood dyscrasias or convulsions that do not result in hospitalization.)
- Suspected transmission of an infectious agent (eg, pathogenic or nonpathogenic) via the study drug is an SAE.

Although pregnancy, overdose, potential drug-induced liver injury (DILI), and cancer are not always serious by regulatory definition, these events must be handled as SAEs.

Any component of a study endpoint that is considered related to study therapy should be reported as an SAE (eg, death is an endpoint, if death occurred due to anaphylaxis, anaphylaxis must be reported).

The following hospitalizations are not considered SAEs in BMS clinical studies:

- a visit to the emergency room or other hospital department < 24 hours, that does not result in admission (unless considered an important medical or life-threatening event)
- elective surgery, planned prior to signing consent
- admissions as per protocol for a planned medical/surgical procedure
- routine health assessment requiring admission for baseline/trending of health status (eg, routine colonoscopy)
- Medical/surgical admission other than to remedy ill health and planned prior to entry into the study. Appropriate documentation is required in these cases.
- Admission encountered for another life circumstance that carries no bearing on health status and requires no medical/surgical intervention (eg, lack of housing, economic inadequacy, caregiver respite, family circumstances, administrative reason).
- Admission for administration of anticancer therapy in the absence of any other SAEs (applies to oncology protocols)

5.3. INTENSITY OF ADVERSE EVENT

The intensity of adverse events should be classified and recorded according to the Common Terminology Criteria for Adverse Events (CTCAE) version 4.03 in the CRF.

5.4. CAUSAL RELATIONSHIP OF ADVERSE EVENT

The causal relationship to study drug is determined by a physician and should be used to assess all adverse events (AE). The causal relationship can be one of the following:

Related: There is a reasonable causal relationship between study drug administration and the AE.

Not related: There is not a reasonable causal relationship between study drug administration and the AE.

The term "reasonable causal relationship" means there is evidence to suggest a causal relationship.

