Objectives	
Primary Objectives:
 
1- To assess the 1-year PFS for patients with RPA class I and II disease treated with nivolumab and IMRT re-irradiation
 
Secondary Objectives:
 
1- Evaluate the OS of patients treated with re-irradiation and nivolumab 2- Evaluate patient QOL 3- Evaluate patterns of failure including rates of locoregional failure and distant failure 4- Identify and estimate the incidence rate of acute and late toxicities associated with combined re-irradiation and nivolumab followed by nivolumab
 
Exploratory Objectives:
 
 • To identify potential biomarkers related to clinical benefit to concurrent nivolumab and re-irradiation in patients with recurrent HNSCC.

SAEStudy Design	
This will be a phase II single arm study of IMRT re-irradiation in combination with nivolumab in the concurrent and maintenance setting. Patients with RPA class I and II based on the recursive partitioning analysis (RPA) classes reported by Ward et al (ASTRO 2016) will be enrolled. The allowable treatment approaches include IMRT. Based on this analysis, only patients with RPA classes I and II will be included; Class III patients will be excluded.
 
RT will be given as 60-66Gy in once daily fractions (2 Gy per fraction).
 
Nivolumab will be administered 2 weeks prior to the beginning of radiation therapy (1 dose at Week -2) and continue every 2 weeks during radiation (4 doses at Weeks 0, 2, 4, 6) for a total of 5 doses. Nivolumab will then be given every 4 weeks for 10 additional doses for a total of 15 doses of Nivolumab.

Number of Patients	
From the MIRI study, the 1-year PFS rate for class I and II combined was 43.8% (95% CI: 38.6 - 49.7%). Assuming a one sided alpha of 0.05 and an 85% power to detect an improvement in 1-yr PFS from 40% to 55% we estimate 46 patients will need to be accrued in 2.5 years and followed for an additional 2 years (estimated maximum total of 51 patients). Accounting for a 20% drop out rate, 62 patients will need to be consented.

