1.1.2. The Role of Reirradiation in HNSCC

With the advent of advanced radiation planning techniques (e.g. IMRT, VMAT), the feasibility and safety of re-irradiation has greatly improved, as has the therapeutic ratio. A recent multi-institutional collaborative study (named MIRI) of over 400 patients treated with IMRT based re-irradiation at 8 institutions, found that the overall acute grade 4-5 toxicity was only 5.6%, and grades ≥ 3 late toxicity was only 13% at two years. Overall, the 2-yr (40%) and 5-yr (22%) survival rates compared favorably to historical data (21). Most importantly, a recursive portioning analysis identified three distinct subgroups of patients with 2-yr OS of 62%, 40% and 17%, respectively, for classes I, II and III (21). This finding underscores the suboptimal outcomes in class III patients (e.g. <2 years between the first and planned second RT courses and in patients with pre-re-irradiation gastrostomy or tracheostomy tubes) for whom prolonged conventionally fractionated IMRT based re-irradiation may not be of benefit. On the other hand, IMRT based re-irradiation produces better results in patients with class I (e.g. >2 yrs between the first and planned second RT courses, and for patients managed with initial resection followed by post-op re-irradiation) and class II disease (e.g. all others), the associated 2 yr overall survival of 50% underscores the need for further improvements to this treatment paradigm in these patients. In a subset analysis of the MIRI collaborative study, the addition of systemic therapy (platinum or cetuximab based) did not appear to positively impact outcomes.

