2.2.3. Secondary Objectives

- 1- Evaluate the 1-yr OS of patients treated with re-irradiation and nivolumab
- 2- Evaluate patient QOL
- 3- Evaluate patterns of failure including local, regional and distant failure rates at 1yr
- 4- Identify and estimate the incidence rate of acute and late toxicities associated with combined re-irradiation and concurrent and adjuvant nivolumab

Exploratory Objectives:

To identify potential biomarkers related to clinical benefit to concurrent and adjuvant nivolumab and re-irradiation in patients with RSP HNSCC.

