5.5. ADVERSE EVENT AND SERIOUS ADVERSE EVENT REPORTING

- All Serious Adverse Events (SAEs) that occur following the subject's written consent to participate in the study through 100 days of discontinuation of dosing must be reported to BMS Worldwide Safety, whether related or not related to study drug. If applicable, SAEs must be collected that relate to any later protocol-specified procedure (eg, a follow-up skin biopsy).
- Following the subject's written consent to participate in the study, all SAEs, whether related or not related to study drug, are collected, including those thought to be associated with protocol-specified procedures. The investigator should report any SAE occurring after these aforementioned time periods, which is believed to be related to study drug or protocol-specified procedure.
- An SAE report should be completed for any event where doubt exists regarding its seriousness;
- If the investigator believes that an SAE is not related to study drug, but is potentially related to the conditions of the study (such as withdrawal of previous therapy or a complication of a study procedure), the relationship should be specified in the narrative section of the SAE Report Form.
- If the BMS safety address is not included in the protocol document (eg, multicenter studies where events are reported centrally), the procedure for safety reporting must be reviewed/approved by the BMS Protocol Manager. Procedures for such reporting must be reviewed and approved by BMS prior to study activation.
- An appropriate SAE form (e.g. ex-US = CIOMS form or USA = Medwatch form) should be used to report SAEs to BMS. The BMS protocol ID number must be included on whatever form is submitted by the Sponsor/Investigator.
 - The CIOMS form is available at: <http://www.cioms.ch/index.php/cioms-form-i>
 - The MedWatch form is available at: <https://www.fda.gov/downloads/AboutFDA/ReportsManualsForms/Forms/UCM048334.pdf>
-
-
- In accordance with local regulations, BMS will notify investigators of all reported SAEs that are suspected (related to the investigational product) and unexpected (ie, not previously described in the IB). An event meeting these criteria is termed a Suspected, Unexpected Serious Adverse Reaction (SUSAR). Investigator notification of these events will be in the form of a SUSAR Report and provided in the FastTrack portal system.

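### Causality is coded only against study drug, so a treatment-related toxicity rate for re-irradiation plus nivolumab cannot be tabulated from the attribution the protocol specifies

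*Combined protocol and SAP*

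**What the plan says.** Section 5.4 gives the only causality scale in the protocol. It is binary, *Related* or *Not related*, and covers every event: "The causal relationship to study drug is determined by a physician and should be used to assess all adverse events (AE"). The negative category is also defined against the drug alone: "There is not a reasonable causal relationship between study drug administration and the AE".

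The fourth secondary objective in section 2.2.3 has a wider subject: "Identify and estimate the incidence rate of acute and late toxicities associated with combined re-irradiation and concurrent and adjuvant nivolumab". The synopsis agrees, referring to "acute and late toxicities associated with combined re-irradiation and nivolumab followed by nivolumab".

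Section 4.5 sits between the two. Its opening sentence is about the drug, "Safety of nivolumab will be evaluated as indicated by intensity and incidence of adverse events", but one of its listed endpoints reads "as well as relatedness of adverse events to treatment", without saying whether treatment means nivolumab, re-irradiation or both.

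Section 8 reports acute and late toxicity as counts and percentages. It applies no relatedness filter and does not split by modality.

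Section 5.5 adds a provision for serious events only. If such an event is judged unrelated to the drug but "is potentially related to the conditions of the study (such as withdrawal of previous therapy or a complication of a study procedure"), the investigator states that relationship in the narrative of the report form.

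**The concern.** The study treatment has two components with overlapping toxicity, and the only coded attribution refers to one of them. The protocol itself expects radiation effects: the note closing section 4.3.2 names dysphagia, dehydration, mucositis and pain at grade 3 as routine in re-irradiation. Dysphagia and pain can also come from tumour.

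At stake is the interpretation of the toxicity objective. An all-cause rate includes disease effects. A rate built on the section 5.4 code is a nivolumab-related rate. The quantity between them, toxicity that the physician ascribes to either part of the study treatment, has no coded variable in the protocol. It matters more here because section 1.1.4 dispenses with a safety run-in, so the toxicity results of this trial are the main evidence on the combination in this setting.

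**Working it through.** No alpha, power, sample size or event figure in the plan depends on attribution, so there is no stated number to reproduce. The check is a comparison of sections, followed by arithmetic for scale.

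**1. Reference treatment in each place**

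| Place | Toxicity is referred to |
|---|---|
| Section 2.2.3 and synopsis | re-irradiation and nivolumab combined |
| Section 4.5, opening sentence | nivolumab |
| Section 4.5, relatedness endpoint | treatment, undefined |
| Section 5.4 | study drug |
| Section 8 | no attribution stated |

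The objective and the coding rule do not refer to the same treatment, and section 4.5 does not settle which applies.

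**2. Three events under section 5.4**

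- Grade 4 mucositis that the physician ascribes to re-irradiation alone: *Not related*.
- Dysphagia that the physician ascribes to tumour regrowth: *Not related*.
- Mucositis with a suspected drug contribution, for example a drug-radiation interaction: may be *Related*, since section 5.4 asks only for evidence suggesting causation.

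The first two share a code although only the first is treatment toxicity.

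**3. What is still collected and counted**

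- The toxicity footnote to the study calendar asks for all grades on the case report forms.
- Section 5.6 collects non-serious events regardless of attribution.
- Section 5.5 collects serious events whether or not they are drug-related.
- Section 8 counts toxicities without a filter.

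A radiation injury coded *Not related* therefore stays in the all-cause incidence. What is missing is its attribution.

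**4. Reach of the serious-event narrative**

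The provision in section 5.5 can rescue some attributions, but it is free text, applies only to serious events, and does not say whether radiation counts as a study procedure. Non-serious events have no equivalent.

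**5. Scale**

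Inputs: 46 required and at most 51 patients (sections 3 and 8); acute grade 4-5 toxicity, where section 1.1.2 says "the overall acute grade 4-5 toxicity was only 5.6" percent; late grade 3 or higher toxicity of 13% at two years (same section). Expected number = n × rate.

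- Acute: 46 × 0.056 = 2.6; 51 × 0.056 = 2.9.
- Late: 46 × 0.13 = 6.0; 51 × 0.13 = 6.6.
- Exact (Clopper-Pearson) 95% interval for 7 of 51 (13.7%): 5.7% to 26.3%. For 6 of 46 (13.0%): 4.9% to 26.3%.
- Moving one patient between codes: 1/46 = 2.2 or 1/51 = 2.0 percentage points.

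With counts this small, how a few events are classified visibly changes any attributed rate.

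**The case against.** The strongest reply is that nothing needed for the objective is lost. Events are recorded with type and grade whatever their cause, section 8 never uses the section 5.4 code, and all-cause incidence is a legitimate and less subjective summary in a single-arm trial of overlapping modalities. The word treatment in section 4.5 can be read to include radiation. Serious events have the narrative, causes of death are a separate endpoint, and events before and after progression could be tabulated separately. The case report forms may already hold a radiation field.

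Most of this stands, and it rules out several stronger readings that a reader might infer:

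- That radiation injuries drop out of the toxicity results. They do not; they remain in the all-cause counts.
- That every event is attributed to nivolumab. Events are assessed against nivolumab, which is different.
- That radiation injury must be coded *Not related*. That follows only when the physician sees no reasonable drug contribution.
- That radiation and tumour effects cannot be told apart at all. For some serious events the narrative may do so; the gap is in coded data.
- That the relatedness endpoint in section 4.5 excludes radiation. It is undefined, not shown to be exclusive.
- That the MIRI rates measure the loss, or show that an attributed rate is the better comparator. Section 1.1.2 does not say how that cohort attributed toxicity, and the cohort included class III patients, whom this trial excludes.
- That the planning rates give the volume of tumour-caused events. One-year PFS of 55% or 40% implies 45% or 60% with progression or death, which is not an adverse event rate.

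None of this supplies the missing variable. Even if treatment in section 4.5 is read to include radiation, the only attribution the protocol defines for filling that endpoint is to the drug.

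**Conclusion.** The point holds in a limited form. Sections 2.2.3, 4.5 and 5.4 refer to different treatments, and the attribution the protocol specifies cannot yield a coded treatment-related rate for the combination. All-cause incidence and nivolumab-related incidence both remain available. The size of the effect on the results cannot be computed from the documents; the counts of about 2.6 to 2.9 acute and 6.0 to 6.6 late events show only that the numbers would be small enough for classification to matter. The conclusion assumes that the forms follow section 5.4 as written. If they already record attribution to radiation, what remains is to bring the text of sections 4.5, 5.4 and 8 into line. This is an inexpensive improvement to the safety reporting and does not touch the primary analysis.

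**What to change.** - **Section 5.4 and the adverse event form:** record relationship separately to nivolumab and to re-irradiation. Leave the nivolumab field unchanged, so that reporting to the drug supplier is unaffected.
- **Section 4.5:** define treatment as either modality, and reword the opening sentence to match.
- **Section 8:** tabulate acute and late toxicity four ways: all-cause, nivolumab-related, re-irradiation-related, and related to either.

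The cost is one extra form field, short text edits and additional table columns. Physicians already judge drug-relatedness under sections 4.3.2 and 4.3.3, so the second judgement is made by the same person at the same time. It is best recorded when the event occurs, which favours making the change early. The drawbacks are slightly more data entry and some subjectivity in attribution; the all-cause table is kept for that reason. No treatment or management rule changes.
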